10.2. Study Termination

Premature termination of this study may occur because of a regulatory authority decision, change in opinion of the Institutional Review Board (IRB); issues with study drug; or at the discretion of the Investigator (or designee), Sponsor, or Sponsor's Medical Monitor if any of the following criteria are met:

- Dose escalation is halted, and no intermediate doses are proposed
- Medical or ethical reasons affecting the continued performance of the study
- Difficulties in the recruitment of subjects
- Cancellation of the drug development program

The Sponsor may suspend dosing or terminate the study at any time for any reason. The Sponsor will notify the Investigator if the study is prematurely terminated. The Investigator must promptly contact all subjects to arrange final study visit(s) and procedures, as directed by the Sponsor.

10.3. Case Report Forms

An electronic case report form (eCRF) is required for each enrolled subject. For screen failure subjects, a minimal set of data will be collected as noted in Section 5.4. Data entered in the eCRF must be consistent with the source documents.

The Investigator has ultimate responsibility for the collection and reporting of all data entered in the eCRF and any other data collection forms and will be electronically signed by the Investigator to attest that the data contained in the eCRF are accurate.

10.4. Source Documents

Source documents provide evidence for the existence of the subject and substantiate the integrity of the data collected. Source documents (e.g., hospital records, patient hard copy/electronic files, clinical/office charts, pharmacy dispensing records, X-rays) are filed at the Investigator's site.

Data entered in the eCRF that are transcribed from source documents must be consistent with the source documents or the discrepancies must be explained. The Investigator may need to request previous medical records or transfer records, depending on the study. Also, current medical records must be available.

Study monitors will perform ongoing source data verification to confirm that data entered into the eCRF by authorized site personnel are accurate, complete, and verifiable from source documents; that the safety and rights of participants are being protected; and that the study is

being conducted in accordance with the currently approved protocol and any other study agreements, International Council for Harmonisation Good Clinical Practice guideline E6 (ICH GCP), and all applicable regulatory requirements.

10.5. Data Protection

Subjects will be assigned a unique identifier by the Sponsor. Any subject records or datasets that are transferred to the Sponsor will contain the identifier only; names or any information which would make the subject identifiable will not be transferred.

The subject must be informed that his/her personal study-related data will be used by the Sponsor in accordance with local data protection law. The level of disclosure must also be explained to the subject, who will be required to give consent for the data to be used as described in the informed consent form (ICF).

The subject must also be informed that medical records may be examined by Clinical Quality Assurance auditors or other authorized personnel appointed by the Sponsor, by appropriate IRB members, and by inspectors from regulatory authorities.

10.6. Recordkeeping

The Investigator agrees to keep and maintain records that would permit the Sponsor and regulatory authorities to evaluate/audit the study. These include the identity of subjects, IRB correspondence, original signed ICFs, source documents, the eCRFs, SAE/Pregnancy Report forms, drug storage/accountability/disposition records, and correspondence (e.g., letters, email, meeting minutes, telephone call records) with the Sponsor or designee. Records should be retained by the Investigator for a minimum of 15 years after completion or discontinuation of the study, according to the ICH guidelines, local regulations, or as specified in the clinical study agreement, whichever is longer.

If the Investigator becomes unable to retain study records for any reason (e.g., retirement, relocation), they must be transferred to the Sponsor or to a designee acceptable to the Sponsor (e.g., another investigator, another institution, or independent third party).

10.7. Quality Control and Quality Assurance

The Sponsor or designee will conduct periodic site visits or audits during or after the study to ensure that the protocol and Good Clinical Practice (GCP) are being followed. The monitors may review the drug storage area, study drug stocks, drug storage/accountability/disposition records, source documents, and regulatory documentation. The Investigator and institution will permit direct access to the physical spaces, records, and source documents to perform this verification to the Sponsor or designee monitors/auditors, IRB members, and appropriate regulatory authority inspectors.

The Investigator must immediately notify the Sponsor or its designee of any regulatory authority inspection notification, will cooperate with the Sponsor or designee to prepare the study site for the inspection, will be present during the inspection along with relevant study staff, will allow the Sponsor or designee to be present during the inspection, and will provide copies of any inspection findings.

10.8. Financial Disclosure

Investigators and sub-investigators will provide the Sponsor with sufficient, accurate financial information as requested to allow the Sponsor to submit complete and accurate financial certification or disclosure statements to the appropriate regulatory authorities. Investigators are responsible for providing information on financial interests of themselves and their family members during the course of the study and for 1 year after completion of the study.

11. ETHICS

11.1. Ethical Conduct of the Study

The study will be conducted in accordance with legal and regulatory requirements, as well as the general principles set forth in the International Ethical Guidelines for Biomedical Research Involving Human Subjects (Council for International Organizations of Medical Sciences 2002), ICH GCP Guidelines, and the Declaration of Helsinki (World Medical Association 1996 and 2008).

In addition, the study will be conducted in accordance with the protocol, ICH GCP, and applicable local regulatory requirements and laws.

11.2. Written Informed Consent

An informed consent form (ICF) meeting the requirements of 21 CFR §50, local regulations, ICH guidelines, Health Insurance Portability and Accountability Act (HIPAA) requirements (where applicable), must be reviewed and approved by the Sponsor, approved by the IRB before use, and available for inspection.

The Investigator or authorized representative will explain the nature of the study to the subject and answer all questions regarding the study. Subjects must be informed that their participation is voluntary, and if they choose to participate, will be required to sign the approved ICF. The medical record must include a statement that written informed consent was obtained before any study procedures were performed, along with the date written consent was obtained. The authorized person obtaining the informed consent must also sign the ICF. The original signed ICF will be retained in the Investigator's records, with a copy provided to the subject.

Subjects must be re-consented to the most current version of the ICF during their participation in the study.

11.3. Institutional Review Board/Independent Ethics Committee

The protocol, protocol amendments, ICF, Investigator's Brochure (IB), and other relevant documents (e.g., advertisements) must be submitted to an IRB by the Investigator and reviewed and approved by the IRB before the study is initiated.

Protocols and any substantial amendments to the protocol will require health authority approval prior to initiation except for changes necessary to eliminate an immediate hazard to study subjects. Any amendments to the protocol will require IRB approval before implementation of changes made to the study design, except for changes necessary to eliminate an immediate hazard to study subjects.

The Investigator will provide written summaries of the status of the study and any other significant safety findings to the IRB annually or more frequently in accordance with its requirements, policies, and procedures. At the end of the study, the Investigator will notify the IRB of the conclusion of the study and its outcome.

12. PUBLICATION POLICY

The results of this study may be published or presented at scientific meetings. If this is foreseen, the Investigator agrees to submit all manuscripts or abstracts to the Sponsor before submission. This allows the Sponsor to protect proprietary information and to provide comments.

The Sponsor will comply with the requirements for publication of study results. In accordance with standard editorial and ethical practice, the Sponsor will generally support publication of multicenter studies only in their entirety and not as individual site data. In this case, a coordinating investigator will be designated by mutual agreement.

Authorship will be determined by mutual agreement and in line with International Committee of Medical Journal Editors authorship requirements.

AESI	Adverse event of special interest
ALP	Alkaline phosphatase
ALT	Alanine aminotransferase
ANC	Absolute neutrophil count
aPTT	Activated partial thromboplastin time
AST	Aspartate aminotransferase
BMI	Body mass index
BUN	Blood urea nitrogen
CK-MB	Creatinine kinase heart
CK-MM	Creatinine kinase skeletal muscle
CrCl	Creatinine clearance
CRU	Clinical research unit
C-SSRS	Columbia suicide severity rating scale
CV%	Percent coefficient of variation
CYP	Cytochrome P450
DRF	Dose-range-finding
ECG	Electrocardiogram
eCRF	Electronic case report form
eGFR	Glomerular filtration rate
EMA	European medicines agency
FEV ₁	Forced expiratory volume in one second
FIH	First-in-human
FSH	Follicle-stimulating hormone
FVC	Forced vital capacity
GGT	Gamma-glutamyl transferase

QMD Ref: Worldwide-TMP-ST-054-1.0_Effective: 12Aug2022	Governing QMD: Worldwide-SOP-ST-026
Confidentiality Statement This document is the property of Worldwide Clinical Trials Inc. and may not be duplicated, copied, altered or removed from company without prior approval from Worldwide Quality Assurance or in compliance with Worldwide Standard Operating Procedures.	

Worldwide Clinical Trials Controlled Quality Management Document			
		Sponsor:	MTR-601-NHV-101
		Protocol Number:	Motric Bio
STATISTICAL ANALYSIS PLAN			

Abbreviation	Definition
HED	Human equivalent dose
HIV	Human immunodeficiency virus
IB	Investigator's brochure
ICF	Informed consent form
INR	International normalized ratio
IP	Investigational product
IRB	Institutional review board
IUD	Intrauterine device
LE	Lower extremity
LVEF	Left ventricular ejection fraction
MAD	Multiple ascending dose
MRSD	Maximum recommended starting dose
MTD	Maximum tolerated dose
NOAEL	No-observed-adverse-effect level
NOS	Nil per os, nothing by mouth
PFT	Pulmonary Function Test
PI	Principal investigator
PD	Pharmacodynamic(s)
PK	Pharmacokinetic(s)
PT	Prothrombin time
QD	Once daily
QTcB	QT interval corrected for heart rate using Bazett's formula
QTcF	QT interval corrected for heart rate using Fridericia's formula
RBC	Red blood cell
SAD	Single ascending dose
SAE	Serious adverse event
SAP	Statistical Analysis Plan

QMD Ref: Worldwide-TMP-ST-054-1.0_Effective: 12Aug2022	Governing QMD: Worldwide-SOP-ST-026
Confidentiality Statement This document is the property of Worldwide Clinical Trials Inc. and may not be duplicated, copied, altered or removed from company without prior approval from Worldwide Quality Assurance or in compliance with Worldwide Standard Operating Procedures.	

Worldwide Clinical Trials Controlled Quality Management Document			
		Sponsor:	MTR-601-NHV-101
		Protocol Number:	Motric Bio
STATISTICAL ANALYSIS PLAN			

Abbreviation	Definition
SAS	Statistical Analysis System
SARS-CoV-2	Severe acute respiratory syndrome coronavirus 2
SOC	System organ class
SRC	Safety review committee
STD	Standard deviation
TEAE	Treatment-emergent adverse events
UE	Upper extremity
ULN	Upper limit of normal

QMD Ref: Worldwide-TMP-ST-054-1.0_Effective: 12Aug2022	Governing QMD: Worldwide-SOP-ST-026

Confidentiality Statement
 
This document is the property of Worldwide Clinical Trials Inc. and may not be duplicated, copied, altered or removed from company without prior approval from Worldwide Quality Assurance or in compliance with Worldwide Standard Operating Procedures.
	

Worldwide Clinical Trials Controlled Quality Management Document			
		Sponsor:	MTR-601-NHV-101
		Protocol Number:	Motric Bio
STATISTICAL ANALYSIS PLAN			

1 INTRODUCTION

This document details the planned statistical analyses for Motric Bio, protocol “MTR-601-NHV-101” study titled “A Randomized, Double-Blind, Placebo-Controlled, First-in-Human, Single and Multiple Ascending Dose Study of MTR-601 in Healthy Volunteers”.

The proposed analyses are based on the contents of the final version 4.0 of the protocol (dated 15-Apr-2024). Exploratory parameters/endpoints will be documented separately in standalone report.

This is a phase 1, randomized, double blind, placebo-controlled, FIH (first in human) study of MTR-601 in normal healthy volunteers will consist of 5 single ascending dose (SAD) level cohorts (including 1 SAD Level 2 Two-Dose cohort), and up to 6 multiple ascending dose (MAD) level cohorts, each comprised of 8 subjects (6 MTR-601; 2 placebo). The current study is a FIH evaluation of MTR-601 and focuses on the safety, tolerability, and pharmacokinetics (including uptake into skeletal muscle) of the drug in normal healthy volunteers. Exploratory assessments of effects on the force of muscular contraction will also be performed and evaluated as it relates to dose, exposure, and/or muscle accumulation with potential adjustments for total body muscle mass.

As a FIH study, this will be conducted in normal healthy volunteers in the fed state, with further evaluation of food effect in SAD dose level 2, as nonclinical studies have indicated that food increases drug exposure. The evaluations of effects on muscular contraction with potential adjustments for total body muscle mass will help guide dosing selection in adult and potential pediatric patient populations in subsequent clinical studies.

The total sample size will be up to 88 subjects to accommodate withdrawal of consent or replacement for other non-TEAE reasons.

QMD Ref: Worldwide-TMP-ST-054-1.0_Effective: 12Aug2022	Governing QMD: Worldwide-SOP-ST-026
Confidentiality Statement This document is the property of Worldwide Clinical Trials Inc. and may not be duplicated, copied, altered or removed from company without prior approval from Worldwide Quality Assurance or in compliance with Worldwide Standard Operating Procedures.	

Worldwide Clinical Trials Controlled Quality Management Document				
			Sponsor:	MTR-601-NHV-101
			Protocol Number:	Motric Bio
STATISTICAL ANALYSIS PLAN				

SAD/MAD Dose Level Cohorts

SAD/MAD Dose Level Cohorts ^a				
SAD/MAD Cohort ^{a & b}	Dose ^g	Fasted	Fed Standard ^c	N ^e
SAD Level 1	10 mg		✓	8 ^f
SAD Level 2, Two-Dose ^d	20 mg	✓	✓	8 ^f
SAD Level 3	40 mg		✓	8 ^f
SAD Level 4	80 mg		✓	8 ^f
SAD Level 5	160 mg		✓	8
MAD Level 1	10 mg		✓	8
MAD Level 2	20 mg		✓	8
MAD Level 3	20 mg		✓	8
MAD Level 4	40 mg		✓	8
MAD Level 5	80 mg		✓	8
MAD Level 6	≤160 mg		✓	8

Abbreviations: MAD = multiple ascending dose; N = number of subjects; SAD = single ascending dose.

[figure not shown]
Fasted: Subjects will remain NPO (clear liquids allowed) for at least 8 hours prior to dosing.

- Subjects will participate in only 1 dose level cohort in either the SAD, Two-Dose, or MAD portions of the study.
- All subjects, regardless of cohort, will have doses administered with staggered timing such that no subjects shall be dosed simultaneously.
- Subjects will be fed a standard (not high-fat) breakfast 30 minutes before dosing.
- Subjects in the SAD Level 2, Two-Dose cohort: For the first dose, subjects will be fasting; for the second dose, subjects will be fed a standard not – high fat breakfast 30 minutes before dosing.
- 6 MTR-601 and 2 placebo per cohort.
- All SAD dose cohorts (including Level 2, Two-Dose) will have 2 sentinel subjects followed at least 72 hours later by the remaining 6 subjects.
- Cohort dose may be modified by the Sponsor based upon pharmacokinetic and safety results from earlier cohorts.

QMD Ref: Worldwide-TMP-ST-054-1.0_Effective: 12Aug2022	Governing QMD: Worldwide-SOP-ST-026
Confidentiality Statement This document is the property of Worldwide Clinical Trials Inc. and may not be duplicated, copied, altered or removed from company without prior approval from Worldwide Quality Assurance or in compliance with Worldwide Standard Operating Procedures.	

Worldwide Clinical Trials Controlled Quality Management Document			
		Sponsor:	MTR-601-NHV-101
		Protocol Number:	Motric Bio
STATISTICAL ANALYSIS PLAN			

Study schema for SAD and MAD as follows:

Motric Bio Study Scheme: Cohorts of 8 participants (6 MTR-601 and 2 placebo) will be sequentially enrolled following evaluation of safety and tolerability (S and T) by a Safety Review Committee (SRC). The SRC will determine whether any dose is safe and tolerable by evaluation of aggregate clinical, laboratory, ECG, echocardiography, spirometry, renal/urinary ultrasonography and PK (as available) data. The Single Ascending Dose (SAD) cohorts will begin dosing with 2 sentinel participants (1:1 - MTR-601: Placebo) followed 72 hours later by dosing the remainder of the cohort (5:1 - MTR-601: Placebo). Dosing will be performed after a standard breakfast, in all but one cohort, as preclinical studies indicated food enhanced exposure. The second SAD cohort will receive two doses of study drug – the first dose will be after overnight fasting and the second dose, following a washout period, after a standard breakfast. The Multiple Ascending Dose (MAD) cohorts will not begin until at least the SAD level 2 two-dose cohort has been completed and will not have sentinel dosing. MAD dosing will be daily for 14 days.

QMD Ref: Worldwide-TMP-ST-054-1.0_Effective: 12Aug2022	Governing QMD: Worldwide-SOP-ST-026
Confidentiality Statement This document is the property of Worldwide Clinical Trials Inc. and may not be duplicated, copied, altered or removed from company without prior approval from Worldwide Quality Assurance or in compliance with Worldwide Standard Operating Procedures.	

Worldwide Clinical Trials Controlled Quality Management Document			
		Sponsor:	MTR-601-NHV-101
		Protocol Number:	Motric Bio
STATISTICAL ANALYSIS PLAN			

2 STUDY OBJECTIVES AND ENDPOINTS

Objectives	Endpoints
Primary	
To assess the safety and tolerability of single and multiple doses of MTR-601 in normal healthy volunteers under fed and fasted conditions.	
The primary endpoint is safety assessed after single and multiple dose administration by:
 
 • Incidence, severity, and relatedness of adverse events (AEs; number and incidence of treatment-emergent adverse events [TEAEs]) • Incidence of laboratory abnormalities, based on hematology, clinical chemistry, coagulation, urinalysis test results • Vital sign measurements • 12-lead electrocardiograms (ECGs) • Echocardiography • Physical and neurological examinations • Telemetry and oximetry • Spirometry • Urinary System Ultrasonography
Secondary	
To evaluate the plasma and urine pharmacokinetics (PK) of MTR-601	
Pharmacokinetic evaluations MAY include:
 
 • Concentration-time relationships • Estimations of dose proportionality at steady state • Estimation of time to achieve steady state based on qualitative evaluation of mean predose concentrations. • PK evaluation of potential MTR-601 metabolites may also be included at the time of analysis

QMD Ref: Worldwide-TMP-ST-054-1.0_Effective: 12Aug2022	Governing QMD: Worldwide-SOP-ST-026

Confidentiality Statement
 
This document is the property of Worldwide Clinical Trials Inc. and may not be duplicated, copied, altered or removed from company without prior approval from Worldwide Quality Assurance or in compliance with Worldwide Standard Operating Procedures.
	

Worldwide Clinical Trials Controlled Quality Management Document			
		Sponsor:	MTR-601-NHV-101
		Protocol Number:	Motric Bio
STATISTICAL ANALYSIS PLAN			

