- Plasma PK samples will be drawn at pre-dose (time 0) on Days 7 and 14; post-dose on Days 7 and 14 at 1, 1.5, 2, 4, 6, 8 and 12 hours; (need trough at D14) 336 hours post-dose (Day 15); 360 hours post-dose (Day 16); and 384 hours post-dose (Day 17). For Cohorts 3-6, PK samples will also be drawn on Day 2 and Day 8 (both pre-dose).
- Urine will be collected for PK analysis on 12-24 hours post-dose on Day 2; Day 7 and 14 from a pre-dose void and post-dose from 0-4 hours, 4-8 hours, 8-12 hours, and 12-24 hours; from 24-48 hours post-dose; from 48-72 hours post-dose; and from 72-96 hours post-dose. Samples are to be collected at intervals under colored lighting into opaque containers to blind participants to any discoloration of the urine.
- Spirometry performed on Days 2, 8, 10, and 12.
- Mandatory muscle biopsy on Day 14 (time 0) only.
- IPSS questionnaire will be performed at the specified timepoints per SOA- results greater than 8 will necessitate an unscheduled urinary system ultrasound as soon as is feasible.
- Urinary system Ultrasound will be performed at day 3, and days 7 and 14 at the 6-hour timepoint unless the IPSS result (greater than 8) necessitates additional unscheduled ultrasonography.
- Serum chemistry, eGFR, and calcium only.

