- Subjects in the SAD Level 2 Two-Dose (20mg) will be dosed in a fasting state on Day 1 with a subsequent 4-day washout period, followed by dosing in a fed state (standard not-high fat breakfast) on Day 6.
- SAD Level 4 (80 mg) dosing is optional and may be adjusted based upon PK and safety results from earlier cohorts.
- Subjects may be enrolled in small groups to accommodate clinic scheduling.

MAD Levels 1–6 dosing:

- The MAD portion of the study will commence at MAD Level 1 (10 mg) after the safe completion of the subjects in at least the 2 SAD Level 2 Two-Dose cohort.
- Subjects in MAD Levels 1–6 will be dosed in a fed state (standard non-high-fat breakfast) over 14 continuous days of dosing.
- MAD cohorts may be enrolled in small groups to accommodate clinic scheduling with subjects dosed in a staggered fashion.

Dose Escalation:

The study will be monitored by a Safety Review Committee (SRC) comprised of the Principal Investigator (PI), the Medical Monitor, and the Sponsor. The SRC is intended to ensure treatment does not pose undue risk to subjects. Dose escalation to the next higher dose level cohort will not take place until the SRC has assessed the data from at least 7 out of 8 subjects/cohort through discharge (supplemental plasma PK information on a previously treated cohort may be requested as a part of the review) and determined that adequate safety and tolerability has been demonstrated to permit proceeding.

The planned dose levels for MAD Cohort 5 (80 mg) and Cohort 6 (160 mg) may be decreased based on the plasma PK from the preceding MAD cohort. Escalation will proceed no higher than a dose that is estimated to yield $\leq \frac{1}{2}$ of the rate 28-day NOAEL exposure ($C_{\max} \leq 421$ ng/mL, $AUC_{0-24} \leq 6,600$ ng*hr/mL).

The SRC may recommend:

- Ascending to the planned next higher dose level
- Ascending to a dose level lower than the planned next higher dosage level cohort
- Repeat dosing at the current dose level
- Descending to an intermediate dose above a previously tolerated dose level
- Pausing dose escalation
- Stopping the study

Participation in the clinical study may be discontinued by an Investigator (or delegate) in charge of the study or by the Sponsor for any of the following reasons in [Table 5](#).

Table 5: Stopping Rules

Stopping Rules ^d	Individual Subject Stopping Rules ^a	Cohort and/or Dose Escalation Stopping Rules
ALT or AST $\geq 3 \times$ ULN	≥ 1 subject	N/A

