AUC_{0-12} (AUC_{tau})	The area under the plasma concentration-time curve from time-zero to 12 hours postdose, calculated by the linear trapezoidal method (Cohorts 1 and 2)
AUC_{0-24} (AUC_{tau})	The area under the plasma concentration-time curve from time-zero to 24 hours postdose (24 h = dosing interval), calculated by the linear trapezoidal method (predose samples collected on Days 2 and 8 will be used as Day 1, 24 h and Day 7, 24 h samples for this calculation)

The following plasma PK parameters will be calculated for MRT-601 after multiple ascending doses (MAD) for Day 14:

Parameter	Definition
$C_{max,ss}$	Maximum observed plasma concentration
$T_{max,ss}$	Time of the maximum plasma concentration

QMD Ref: Worldwide-TMP-ST-054-1.0_Effective: 12Aug2022	Governing QMD: Worldwide-SOP-ST-026
Confidentiality Statement This document is the property of Worldwide Clinical Trials Inc. and may not be duplicated, copied, altered or removed from company without prior approval from Worldwide Quality Assurance or in compliance with Worldwide Standard Operating Procedures.	

Worldwide Clinical Trials Controlled Quality Management Document			
		Sponsor:	MTR-601-NHV-101
		Protocol Number:	Motric Bio
STATISTICAL ANALYSIS PLAN			

Parameter	Definition
AUC_{τ}	The area under the plasma concentration-time curve over the 24 h dosing interval, calculated by the linear trapezoidal method
C_{avg}	Average plasma concentration over the 24 h dosing interval, calculated as: $C_{avg} = AUC_{\tau}/\tau$
C_{last}	Last quantifiable plasma concentration
T_{last}	Time of the last quantifiable plasma concentration
CL_{ss}/F	The apparent total clearance at steady-state after extravascular administration, calculated as: $CL_{ss}/F = \text{Dose}/AUC_{\tau}$, where F is the bioavailability
V_z/F	The apparent volume of distribution at steady-state after extravascular administration, calculated as: $V_z/F = \text{Dose}/(AUC_{\tau} \times \lambda_z)$, where F is the bioavailability
R_{AUC}	Accumulation ratio of AUC_{τ} , calculated as: $AUC_{\tau} (\text{Day 14})/AUC_{0-24} (\text{Day 1})$ for Cohorts 3 onward only
$R_{C_{max}}$	Accumulation ratio of C_{max} , calculated as: $C_{max} (\text{Day 14})/ C_{max} (\text{Day 1})$

The following urine PK parameters will be calculated for MRT-601 (SAD, MAD, Day 1, 7, and 14):

Parameter	Definition
-----------	------------

QMD Ref: Worldwide-TMP-ST-054-1.0_Effective: 12Aug2022	Governing QMD: Worldwide-SOP-ST-026

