5.14 Pharmacokinetic Analyses

5.14.1 Concentration-Time Data

5.14.1.1 Plasma

MRT-601 plasma concentration-time data will be tabulated by nominal time and treatment (dose level) for SAD and by nominal time, treatment (dose level), and study day for MAD using descriptive statistics. For presentation of the individual data and summary statistics, concentrations below the limit of quantitation (BLQ) will be set to zero. Nominal and relative time will be presented in hours.

MRT-601 samples will be collected at:

SAD: 0 (pre-dose) and at 0.25, 0.50, 1, 1.5, 2, 4, 6, 8, 12, 24, 48, 72, and 96 hours post-dose.

SAD (2 dose, food effect): 0 (pre-dose 1) and at 0.25, 0.50, 1, 1.5, 2, 4, 6, 8, 12, 24, 48, 72, and 96 hours postdose

MAD, Day 1: 0 (predose) and at 0.25, 0.50, 1, 1.5, 2, 4, 6, 8, and 12 hours postdose for Cohorts 1 and 2. A 24 hour sample (Day 2, predose) was added for Cohort 3 onward.

QMD Ref: Worldwide-TMP-ST-054-1.0_Effective: 12Aug2022	Governing QMD: Worldwide-SOP-ST-026
Confidentiality Statement This document is the property of Worldwide Clinical Trials Inc. and may not be duplicated, copied, altered or removed from company without prior approval from Worldwide Quality Assurance or in compliance with Worldwide Standard Operating Procedures.	

Worldwide Clinical Trials Controlled Quality Management Document			
		Sponsor:	MTR-601-NHV-101
		Protocol Number:	Motric Bio
STATISTICAL ANALYSIS PLAN			

MAD Day 7: 0 (predose) and at 0.25, 0.50, 1, 1.5, 2, 4, 6, 8, and 12 hours postdose for Cohorts 1 and 2. A 24 hour sample (Day 8, predose) was added for Cohort 3 onward.

MAD Day 14: 0 (pre-dose) and at 0.25, 0.50, 1, 1.5, 2, 4, 6, 8, 12, 24, 48, 72, and 96 hours post-dose.

Mean plasma concentration-time data will be presented graphically on linear and semi-logarithmic scales using nominal times. Individual subject concentration-time data will be presented graphically on linear and semi-logarithmic scales using actual times. For individual subject concentration-time data, spaghetti plots (all subjects in one plot per treatment) and all treatments in one plot for each subject will be created.

For SAD, mean profiles and spaghetti plots will be created.

For SAD (food effect): mean profiles, spaghetti plots, and individual plots (fed vs. fasted) will be created.

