16.2.6.3	MRT-601 Urine Concentrations, Volume, Ae, Fe, and Fe% Listing by Subject (SAD) – PK Population	MR	
16.2.6.4	MRT-601 Urine Concentrations, Volume, Ae, Fe, and Fe% Listing by Subject (MAD) – PK Population	MR	
16.2.6.5	Terminal Elimination Rate for MRT-601 for Individual Subjects (SAD) – PK Population	MR	
16.2.6.6	PK Output Text (SAD) - Plasma	MR	
16.2.6.7	PK Output Text (MAD) - Plasma	MR	
16.2.6.8	PK Output Text (SAD) - Urine	MR	
16.2.6.9	PK Output Text (MAD) - Urine	MR	
16.2.6.10	SAS Output Text – Dose Proportionality Assessment (SAD)	MR	

QMD Ref: Worldwide-TMP-ST-054-1.0_Effective: 12Aug2022	Governing QMD: Worldwide-SOP-ST-026
Confidentiality Statement This document is the property of Worldwide Clinical Trials Inc. and may not be duplicated, copied, altered or removed from company without prior approval from Worldwide Quality Assurance or in compliance with Worldwide Standard Operating Procedures.	

Worldwide Clinical Trials Controlled Quality Management Document			
		Sponsor:	MTR-601-NHV-101
		Protocol Number:	Motric Bio
STATISTICAL ANALYSIS PLAN			

Listing Number	Listing Title	Validation Method	Shell Number (if repeat)
16.2.6.11	SAS Output Text – Dose Proportionality Assessment (MAD)	MR	
16.2.6.12	SAS Output Text – Food Effect Assessment	MR	
16.2.7	Adverse Event Listings		
16.2.7.1	Adverse Event Data - Safety Population	IP	
16.2.7.2	Serious Adverse Event Data- Safety Population	IP	
16.2.8	Individual Laboratory Measurements and Other Safety		
16.2.8.1	Hematology Data - Safety Population	IP	
16.2.8.2	Serum Chemistry Data - Safety Population	IP	
16.2.8.3	Urinalysis Data - Safety Population	IP	
16.2.8.4	Coagulation Data - Safety Population	IP	
16.2.8.5	Cystatin C Data - Safety Population		
16.2.8.6	Covid-19 Test Data - Safety Population	IP	
16.2.8.7	Serology Data - Safety Population	IP	
16.2.8.8	Pregnancy Test Data - Safety Population	IP	
16.2.8.9	FSH (Follicle Stimulating Hormone) Data - Safety Population	IP	
16.2.8.10	Urine Drug, Alcohol and Cotinine Screen Data - Safety Population	IP	
16.2.9.1	Vital Signs Data - Safety Population	IP	
16.2.9.2	Lead ECG Data - Safety Population	IP	
16.2.9.3	Lead ECG Data (Overall Interpretation) - Safety Population	IP	
16.2.9.4	Physical Examination Data - Safety Population	IP	
16.2.9.5	Neurological Examination Data - Safety Population	IP	
16.2.9.6	Cardiac Telemetry Collection Data - Safety Population	IP	
16.2.9.7	Oximetry Collection Data - Safety Population	IP	

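### With no plasma sample on MAD Days 3 to 6, the trough reading probably gives only a coarse bracket for time to steady state, and lambda-z and T1/2 are missing from the MAD Day 14 list

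*SAP*

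**What the plan says.** SAP section 2 lists the secondary PK evaluations under the lead-in "Pharmacokinetic evaluations MAY include". One of them is "Estimation of time to achieve steady state based on qualitative evaluation of mean predose concentrations". MAD subjects are dosed once daily "over 14 continuous days of dosing" (Protocol 4.1).

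The troughs available for that reading come from the plasma PK footnote to Protocol Table 3:
- All MAD cohorts: "Plasma PK samples will be drawn at pre-dose (time 0) on Days 7 and 14", with a further sample on Day 15, 24 h after the last dose.
- Later cohorts: "For Cohorts 3-6, PK samples will also be drawn on Day 2 and Day 8 (both pre-dose". SAP 5.14.1.1 agrees for the first of these: "A 24 hour sample (Day 2, predose) was added for Cohort 3 onward".

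On parameters, SAP 5.2.12 lists lambda-z and T1/2 for SAD. Neither appears in the MAD lists for Days 1 and 7 or for Day 14. The Day 14 list does contain Vz/F, described as "The apparent volume of distribution at steady-state after extravascular administration, calculated as" dose over the product of AUCtau and lambda-z. SAP 5.14.2 gives acceptance criteria for lambda-z and promises a separate listing. In SAP section 10 that listing (16.2.6.5) is titled "Terminal Elimination Rate for MRT-601 for Individual Subjects (SAD"), and the terminal-regression figure (14.4.5.1) is also for single doses only.

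**The concern.** Troughs can date the arrival at steady state only if some are taken while concentrations are still rising. Cohorts 3-6 have one early trough (Day 2) and then nothing until Day 7. Cohorts 1-2 have nothing after 12 h on Day 1 until Day 7. If the rise is essentially over by Day 7, the later troughs confirm a plateau but do not show when it began.

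Half-life from the multiple-dose data is the natural cross-check, and Day 14 is sampled well past the dosing interval. The SAP does not list it for MAD, so a reader of the report would have a wide interval and no planned multiple-dose estimate to narrow it. The lambda-z gap is also an internal inconsistency, because Day 14 Vz/F cannot be computed from the parameters listed beside it.

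**Working it through.** **Inputs.** The dosing interval is 24 h (SAP 5.2.12). Accumulation at steady state is below 2-fold, from the interim review of MAD 10 and 20 mg (Protocol 2.3). That figure cannot be reproduced, because the documents give neither concentrations nor a half-life, so it is used as an upper bound. Assumption: one-compartment linear accumulation with absorption short relative to 24 h.

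**Formulas.** With accumulation ratio R:
- k = -ln(1 - 1/R) / 24
- effective half-life = ln 2 / k
- time to 90% of steady state, t90 = ln 10 / k = 3.32 x half-life
- pre-dose level on Day d as a share of the steady-state trough = 1 - (1 - 1/R)^(d-1)

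**Example.** For R = 2, k = ln 2 / 24, so the half-life is 24 h and t90 = 3.32 x 24 = 79.7 h. The Day 2 trough is 1 - 0.5 = 50% of steady state, and the Day 7 trough is 1 - 0.5^6 = 98.4%.

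| R | Half-life (h) | t90 (h) | Day 2 | Day 3 | Day 4 | Day 5 | Day 7 |
|---|---|---|---|---|---|---|---|
| 1.11 | 7.2 | 24.0 | 90.0% | 99.0% | 99.9% | 100.0% | 100.0% |
| 1.2 | 9.3 | 30.8 | 83.3% | 97.2% | 99.5% | 99.9% | 100.0% |
| 1.5 | 15.1 | 50.3 | 66.7% | 88.9% | 96.3% | 98.8% | 99.9% |
| 2.0 | 24.0 | 79.7 | 50.0% | 75.0% | 87.5% | 93.8% | 98.4% |

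**Where the method stops discriminating.**
- The Day 2 trough equals 1/R. It is already at 90% when R is 1/0.9 = 1.11 or less (half-life 7.2 h or less).
- The Day 7 trough is below 90% only if the half-life exceeds 144/3.32 = 43 h, which means R above 3.1.
- Between those limits the 90% crossing falls in the unsampled stretch. R from 1.11 to 2 lies wholly inside it. Taking 95% as the mark instead, the lower limit moves to R = 1.05, and t95 at R = 2 is 104 h, still before Day 7.

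So R = 1.2 (t90 of 31 h) and R = 2 (t90 of 80 h) give the same trough-based answer.

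**Day 14 terminal phase.** SAP 5.14.1.1 samples to 96 h after the last dose, and the Table 3 grid marks plasma PK on Day 18. The Table 3 footnote ends at 384 h, which is Day 17. The Day 14 dose falls at 13 x 24 = 312 h, so this is 384 - 312 = 72 h after it. From 24 h onward that is three points under the footnote and four under the grid and the SAP. SAP 5.14.2 requires at least three for lambda-z.

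**The case against.** The strongest reply is that the evaluation is answerable, if coarsely, and that little depends on it. Much of this stands.

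A reader might infer that the method can only ever return Day 7, whatever the drug does. The documents do not support that. With Cohorts 3-6 sampled on Days 2, 7, 8, 14 and 15, R at or below 1.11 would read as by Day 2. A half-life of 48 or 72 h would put Day 7 at 87.5% or 75% and Day 14 at about 99% or 95%, which would read as after Day 7. Those half-lives imply R of 3.4 and 4.8, which the interim figure excludes at 10 and 20 mg. That figure has not been shown for multiple doses of 40 mg and above, so the Day 7, 8 and 14 comparison is a real check there.

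A reader might also infer that half-life has been discarded. It has not. SAD T1/2 is planned with sampling to 96 h, R_AUC is planned from Cohort 3, and the lambda-z criteria in SAP 5.14.2 are not restricted to SAD. Vz/F on Day 14 presupposes lambda-z. The accurate description is that lambda-z and T1/2 are not listed for MAD.

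It is also true that the reading is declared qualitative, that no hypothesis is tested (Protocol 9.1), that the escalation cap is set on Cmax and AUC0-24, and that steady-state dose proportionality uses Day 14, where the plateau is not in doubt under this model.

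The objection does not remove the sampling gap, the width of the resulting bracket, or the missing parameter rows.

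**Conclusion.** The concern holds, at minor severity. If accumulation is below 2-fold and kinetics are roughly one-compartment, 90% of steady state is reached by about 80 h. For R above about 1.11 the planned reading then returns only after Day 2 and by Day 7 in Cohorts 3-6, or by Day 7 in Cohorts 1-2.

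This rests on two things the documents do not settle: the kinetic model, and the carry-over of a 10-20 mg interim figure to higher doses. A slow terminal phase could change the timing. The missing trough days and the absent MAD lambda-z and T1/2 rows rest on neither.

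Nothing here touches the primary safety objective or an escalation decision. What makes it worth changing is that samples and a ratio already planned would give a sharper answer than the method written down.

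**What to change.** Two SAP text changes, with no new samples for either:

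1. **Day 14 parameters.** Add lambda-z and T1/2 to the MAD Day 14 list in SAP 5.2.12, under the existing 5.14.2 criteria. Extend Listing 16.2.6.5 and Figure 14.4.5.1 to MAD. Reconcile the last Day 14 plasma sample between the Table 3 footnote (Day 17, 72 h) and the Table 3 grid and SAP (Day 18, 96 h).
2. **Time to steady state.** Report the trough-based result as an interval. For Cohort 3 onward, supplement it with an effective half-life from the cohort geometric mean R_AUC and its 90% CI: 24 x ln 2 / ln(R/(R-1)). Time to 90% of steady state is 3.32 x that value. State the one-compartment assumption. The formula increases with R, so the CI limits carry over directly; where R or a limit is 1 or less, report it as not estimable.

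Use the cohort mean and not individual ratios. As an illustration, assume lognormal ratios, independent days, 6 active subjects and within-subject CV of 10% to 20%. At a true R of 1.2, 10% to 26% of subjects would then show R of 1 or less, and the chance of at least one in a cohort would be 46% to 83%. Dropping them would bias half-life upward.

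The cost is one stated model assumption and a little more analysis. Extra PK tubes at the Day 3-6 chemistry draws are not recommended: Table 3 gives no hour for those draws, so they may not be pre-dose, and the change would need a protocol amendment and IRB approval.
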